Choice of therapy for GSM depends on symptom severity and treatment efficacy and safety. First-line treatment for symptomatic women with GSM, recommended by the North American Menopause Society, includes vaginal moisturizers, vaginal lubricants, and continued sexual activity. If these therapies fail, estrogen treatment should be considered in patients without contraindications. Topical estrogen therapy is designed to temporarily alleviate symptoms and reverse atrophic anatomical changes [14]. Despite proven effectiveness with symptom relief [14, 15], compliance rates for estrogen are variable, ranging between 52-74% [16]. Furthermore, long-term data (> 1 year) of these topical estrogen therapies are lacking. [15]. Additionally, no information is available in high-risk patients [14], e.g. those with known breast or uterine cancer in whom estrogen therapy is relatively contraindicated and where the management depends on a woman's preference, potential benefits, understanding of potential risks, and recommendations from oncology specialists [14].

Fractional CO₂ lasers have demonstrated safety and remodeling tissue properties in many body regions, such as the skin of the face, neck and chest, with the effect of producing new collagen and elastic fibers [17-20]. Moreover reports on the use of Er:YAG laser, similar to a CO₂ laser for its superficial effect, showed improvement in two aspects of pelvic floor dysfunction (urinary incontinence and vaginal laxity) [21,22]. Recently, the regenerative effects of intravaginal fractional CO₂ laser on the vaginal epithelium and lamina propria in postmenopausal women with GSM has been reported by Salvatore *et al* [23]. The same investigators found that microablative fractional CO₂ laser was feasible, efficacious, and safe in improving GSM symptoms in postmenopausal women at 12-week follow-up [24]. Additionally, intravaginal fractional CO₂ laser therapy caused a significant decrease in the severity of dyspareunia related to vaginal dryness in these patients, and was subsequently associated with a consistent improvement in sexual function and sexual satisfaction of menopausal women with GSM [25, 26].

Hypothesis: The CO₂ fractional vaginal laser therapy is non-inferior to vaginal estrogen therapy in the treatment of GSM.

Study Design and Aim:

This is a multi-centered, randomized prospective single blinded clinical trial comparing CO2 fractionated vaginal laser therapy and vaginal estrogen therapy in the treatment of vulvovaginal atrophy/GSM

Study Outcomes:

The primary outcome is subjective improvement of vaginal dryness using a 10 cm Visual analog scale.

The secondary outcomes that will be assessed include

1. An objective evaluation of vaginal atrophy/estrogenization measured by the globally validated “Vaginal Health Index” (VHI) score [reference Bachmann Maturitas 1995 attached]
2. The effect of GSM symptoms on QoL using the DIVA questionnaire [28]
3. The effect of treatment on the vaginal maturation index, at baseline and 6 month follow up
4. The effect of treatment on vaginal wall elasticity, using standard vaginal dilators to determine vaginal caliber
5. The effect of treatment on the female sexual function, by means of the Female Sexual Function Index (FSFI)[29]
6. Calculation of the percentage of patients who are sexually active or resume intercourse after therapy. A sexual function question not included in FSFI has been added to evaluate this.
7. The effect of the treatment on urinary symptoms by means of the Urogenital Distress Inventory (UDI-6) [30]
8. The degree of difficulty encountered by the physician in performing the MonaLisa laser treatment assessed via a 5-point Likert scale,
9. The rate of satisfaction of patients with treatment assessed by the Patient Global Impression of Improvement (PGI), using a 5-point Likert scale.

Subject SelectionInclusion Criteria

- Menopausal with absence of menstruation for at least 12 months
- Presence of vaginal atrophy symptoms [subjective assessment of vaginal dryness ≥ 7 cm on VAS)
- Prolapse stage \leq II, according to the pelvic organ prolapse quantification (POP-Q) system[31]
- No pelvic surgery within 6 months prior to treatment (vulva biopsy may be included after 2 weeks)
- Understanding and acceptance of the obligation to return for all scheduled follow-up visits

- English speaking and able to give informed consent

Exclusion Criteria

- Personal history of vulvovaginal condyloma, vaginal intraepithelial neoplasia (VAIN), vaginal carcinoma, lichen sclerosis, lichen planus, history of vaginal radiation, history of cervical cancer, other gynecologic cancer, or pelvic radiation
- Acute or recurrent urinary tract infection (UTI), or genital infection (e.g. bacterial; vaginosis, herpes genitalis, candida).
- Personal history of Scleroderma
- Any serious disease, or chronic condition, that could interfere with the study compliance
- Previously undergone reconstructive pelvic surgery within the past 6 months
- Previously undergone reconstructive pelvic surgery with transvaginal mesh kits and sacrocolpopexy with synthetic mesh for prolapse, excluding synthetic slings (unless current untreated exposure or extrusion)
- Have used vaginal estrogen cream, ring or tablet within 1 month prior to entering the study
- Vaginal moisturizers, lubricants or homeopathic preparations within 2 weeks of therapy
- Personal history of thrombophlebitis
- Personal history of heart failure or myocardial infarction within 12 months of procedure
- Use or anticipated use of antiplatelet therapy, anticoagulants, thrombolytics, vitamin E or nonsteroidal anti-inflammatory drugs within 2 weeks pre-treatment
- Contraindication to vaginal estrogen therapy
- Unwilling to Take vaginal estrogen therapy
- Inability to give informed consent

Subject Recruitment and Screening

Study subjects will be recruited from patients who present to the clinical sites at the Women's Health Institute at the Cleveland Clinic, Christ Hospital, Stanford University Hospital, MedStar Washington Hospital Center, Women's and Infants' Hospital of Rhode Island and Wake Forest School of Medicine for treatment of GSM. Cleveland Clinic will serve as the central Data Coordinating Center

Study Identification and Recruitment

Potential subjects will be identified by members of the sections of Urogynecology and Reconstructive Pelvic Surgery and Benign Gynecology at the respective institutions. Eligible patients who agree to participate will be provided written informed consent administered by the collaborators listed on this IRB.

Randomization

The participants will then be randomized to either fractional CO2 vaginal laser therapy or vaginal estrogen therapy according to a computer-generated randomization schedule with random block sizes with the use of the SAS statistical software package (SAS Institute, Cary, NC). All patients will be unblinded to their assignment.

Diagnostic and Therapeutic Interventions

In addition to a standardized evaluation including the history and physical examination, patients will be asked to complete the Female Sexual Function Inventory (FSFI) questionnaire, the Day-to-day Impact of Vaginal Aging (DIVA) questionnaire, and the Urogenital Distress Inventory (UDI-6), at baseline, 3 months, and 6 months after baseline and visual analog scales (VAS) for GSM symptoms. The Patient Global Index (PGI) will also be administered at 6 months. Completion of these questionnaires should take no more than 15-20 minutes. A vaginal maturation index will be obtained at the baseline visit on a regular Pap Smear slide and fixed with cytofixative and air dried. This will be repeated during the last follow up visit at 6 months.

Vaginal Laser Protocol

Postmenopausal women will undergo treatment intravaginally with the fractional microablative CO₂ laser system (SmartXide 2 V 2 LR, MonaLisa Touch, DEKA, Florence, Italy), using the following setting: dot power 30 watt, dwell time 1000 μ s, dot spacing 1000 μ m and the smart stack parameter from 1 to 3. Stack 1 is used at baseline and stack 3 at 6 weeks and 3 months. The laser beam will be applied using a 90° vaginal probe gently inserted up to the top of the vaginal canal and subsequently withdrawn at centimeter intervals and rotated to 6 positions in an alternating clockwise and counterclockwise pattern in order to provide a complete treatment of the vaginal wall. At the investigators discretion a flat probe (vulvar probe) may be utilized to more efficiently treat the introital area and vestibule. At the level of the vaginal introitus, the dot power will be decreased to 26 watts. A treatment cycle includes three laser applications (every 40-50 days, approximately 6 weeks). The procedure will be performed in the outpatient clinic and does not require any specific preparation (e.g. analgesia/anesthesia). At the clinician's discretion, EMLA cream may be applied to introitus for thirty minutes and wiped clean and dried prior to vulvar laser therapy. Patients will be recommended to avoid coital sexual activity for at least 3 days after each laser application because a mild inflammatory reaction may last up to 48 hours after laser therapy. Topical lidocaine 5% ointment may be used for any vulvar pain post-procedure.

Post Treatment Instructions

- Each subject shall be evaluated immediately post-treatment for complications and side effects, excessive bleeding, symptomatic vaginal discharge, pain, etc.
- Each study subject will be asked to assess discomfort of treatment using a 5-point Likert scale.
- The patient will be instructed on the specific activity limitations following the procedure, sedentary activities are recommended for a least a few days.
- The subject will not engage in vigorous exercise or contact sports for at least 72 hours, or until approved by the physician.
- The subject will refrain from douching for at least 72 hours after the procedures.
- Subjects will not engage in intercourse for at least 72 hours post procedure.
- The subject may shower but may not bathe the day following the procedure. They will use regular shower gel or soap.

Vaginal Estrogen Protocol

The women in the vaginal estrogen group will be prescribed and asked to administer one of three common choices of vaginal estrogen therapy based on patient's formulary and preference of cream or tablet form:

- 1) Conjugated estrogen cream (Premarin[®]): 0.5 g of cream intravaginally daily (using applicator or fingertip) for two weeks (fourteen days) then 0.5 g twice weekly for 24 ± 2 additional weeks, **or**
- 2) Estradiol cream (ESTRACE[®]): 1.0 g of cream intravaginally daily (using applicator or fingertip) for two weeks (fourteen days) then 1.0 g twice weekly for 24 + 2 additional weeks, **or**
- 3) Estradiol vaginal tablet (Vagifem[®]): one tablet (10 microgram) inserted daily into the vagina for two weeks (fourteen days) then 1 tablet inserted intravaginally twice weekly for 24 + 2 additional weeks.

Vaginal examinations

Vaginal Health Index (VHI) score including vaginal pH will be obtained using litmus paper during baseline and each follow-up examination and recorded. This will be obtained during baseline, 6 week, 3 month, and 6 month follow-up by a **blinded examiner** prior to assessment of vaginal wall elasticity with silastic dilators. A limited vaginal exam will be performed to assess the condition of the vaginal area. This exam will include a vaginal calibration, performed with a standard vaginal dilator (Syracuse Medical). The investigator will determine the largest dilator of the five sizes available (XS, S, M, L, XL), that the subject can comfortably have placed in her vagina. The subject then assesses how much pain she is experiencing when the dilator is placed in her vagina, using a 5-point Likert scale.

- GSM symptom (vaginal dryness, vaginal burning, vaginal itching, dysuria) will be assessed using the VAS.
- Patient evaluation of the overall treatment (PGI) using a 5-point Likert scale will be conducted at 6 week, 3 month and 6 month follow-up visits.
- After each treatment, the PI or co-investigator will be asked to evaluate the ease of treatment using a 5-point Likert scale.
- After each treatment, the subject will be asked the degree of discomfort experienced as a result of treatment using a 5-point Likert scale.
- Events will be evaluated and recorded.

Questionnaires and evaluations

Questionnaires will be administered by a **research nurse coordinator who is blinded to the patient's therapy**. Sexual function, GSM, and urinary function will be evaluated with the 10-cm VAS, Female Sexual Function Index (FSFI), Day-to-day Impact of Vaginal Aging (DIVA), and Urogenital Distress Inventory (UDI-6), both at baseline prior to 1st laser treatment or commencing with vaginal estrogen (depending on treatment group), and at 12 weeks from

baseline (+/- 1 week) but prior to 3rd laser treatment (if applicable), and at 3 months follow-up after 3rd laser treatment (if applicable). Note that all patients will follow up 6 months from baseline visit for final assessment

The DIVA questionnaire will be administered at baseline, 3 month, and 6 month follow-up visit period, in addition to the FSFI, UDI-6, VHI, and PGI during final assessment. All questionnaires are supplied in the appendix.

Calendar of Study Procedures

	Baseline	6 weeks	3 months	6 months
Informed Consent	X			
H & P	X			
MonaLisa Touch vaginal laser ¹	X	X	X	
Vaginal estrogen therapy ^{2, 3, 4}	X	X	X	
Vaginal symptom VAS	X	X	X	X
Vaginal health index VHI	X	X	X	X
Vaginal maturation index	X			X
DIVA questionnaire	X		X	X
Vagina dilator calibration	X	X	X	X
FSFI	X		X	X
UDI-6	X		X	X
Likert scale (laser patient)	X	X	X	
PGI		X	X	X
Likert scale (laser provider ease)	X	X	X	
Adverse events	X	X	X	X
Sexual activity	X	X	X	X

¹A treatment cycle includes three laser applications (every 5-7 weeks).

²Conjugated estrogen cream (Premarin[®]): 0.5g of cream intravaginally daily (using applicator or fingertip) for two weeks (fourteen days) then 0.5 g twice weekly for 24 ± 2 additional weeks, **or**

³Estradiol cream (ESTRACE[®]): 1.0 g of cream intravaginally daily (using applicator or fingertip) for two weeks (fourteen days) then 1.0 g twice weekly for 24 + 2 additional weeks, **or**

⁴Estradiol vaginal tablet (Vagifem[®]): one tablet (10 microgram) inserted daily into the vagina for two weeks (fourteen days) then 1 tablet inserted intravaginally twice weekly for 24 + 2 additional weeks.

Data Collection & Management:

Baseline data will include the following:

- Patient age, race, vaginal parity, menopausal state, BMI, history of previous use of vaginal estrogen
- FSFI, DIVA, and UDI-6 questionnaires
- VAS for GSM symptoms and VHI for objective GSM findings

Data points recorded during the procedure will include:

- Likert Scales for physician assessment of patient comfort during the procedure.
- Adverse events including inability to complete the procedure due to discomfort or constricted vagina

Post-procedure data will include the following:

- The rate of satisfaction of patients with treatment by mean of the Patient Global Impression of Improvement (PGI), using a 5-point Likert scale.
- The degree of difficulty encountered by the physician in performing the treatment, by mean of a 5-point Likert scale.
- Additionally, untoward side effects of treatment such as new bothersome vaginal irritation and significant vaginal bleeding will be recorded.

Protection of each subject's personal health information will be a priority in this study. One master Excel file containing subject personal information including name and medical record number will be kept in a password-protected file, on a designated protected research drive on a password-protected computer in a locked office at each respective institution. In that file, each subject will be assigned a subject identification number that will be used for the purposes of data collection in order to de-identify subjects.

All paper forms used for data collection will be kept in a research cabinet dedicated to this project, which will be locked at all times, in a locked office at the Cleveland Clinic (or other institution). All forms will contain de-identified information. Identification numbers will correspond to the subjects listed in the master excel file.

All study data will be transferred and managed electronically using REDCap (Research Electronic Data Capture). Each subject will be entered into REDCap using the assigned identification number from the master excel file. REDCap is a secure, web-based application designed to support data capture for research studies, providing user-friendly web-based case report forms, real-time data entry validation, audit trails, and a de-identified data export mechanism to common statistical packages. The system was developed by a multi-institutional consortium which was initiated at Vanderbilt University and includes the Cleveland Clinic. The

database is hosted at the Cleveland Clinic Research Datacenter in the JJN basement and is managed by the Quantitative Health Sciences Department. The system is protected by a login and Secure Sockets Layers (SSL) encryption. Data collection is customized for each study as based on a study-specific data dictionary defined by the research team with guidance from the REDCap administrator in Quantitative Health Sciences at the Cleveland Clinic.

Statistical Analysis Plan

Sample Size Rationale

We plan to enroll and randomize 196 patients in this non-inferiority trial comparing vaginal estrogen therapy to laser treatment of vaginal atrophy. The primary outcome will be subjective assessment of vaginal dryness as assessed by 10 cm visual analog scale at 6 months after initiating treatment. Assuming an alpha of 0.025 and a standard deviation of 2.0 [24], 85 subjects in each group will provide a 90% power to reject the null hypothesis (H0) that the true difference in vaginal dryness VAS score (Vaginal Estrogen – Vaginal Laser) is less than or equal to 1.0 cm on the VAS (effect size 0.5) in favor of the alternative hypothesis (H1): the true difference is greater than 1.0 cm using a one sided two sample t-test. Anticipating a 15% loss to follow-up and/or drop-rate over the period of the study, the total enrollment goal is 196 participants.

Analysis Plan

This study is a non-inferiority study design. The predefined non-inferiority margin is a difference of 1.0cm on a 10cm VAS. To minimize bias towards a finding of non-inferiority, data from women who were eligible and received the assigned treatment (per protocol) will be used for the analysis of the primary outcome. The primary outcome will be presented as the difference in VAS scores between treatments (Vaginal Estrogen – Vaginal Laser). The hypothesis of non-inferiority of the two treatment groups will be tested by comparing the lower limit of the two-sided 95% confidence interval (equivalent of a one-sided significance level of 0.025%) of the absolute difference with the margin set at -1.0cm. A secondary analysis of the primary outcome according to original treatment assignment (intent to treat) will also be performed as well as standard superiority testing using Student's t-test. If differences in baseline patient characteristics are noted, linear regression analysis adjusting for these differences will also be performed. Secondary outcomes will be analyzed using the intent to treat population using Pearson's Chi-square test for categorical data, Student's t-test for parametric continuous data, or Wilcoxon rank sum test for ordinal or nonparametric continuous data. Changes in patient reported outcome questionnaires (FSFI, DIVA, UDI-6, etc.) will be compared between treatments using repeated measures ANCOVA.

SAFETY AND ADVERSE EVENTS

Definitions

Adverse events include prolonged vaginal bleeding beyond 48 hours, heavy vaginal bleeding, bothersome vaginal irritation, bacterial vaginosis, vaginal yeast infection, post-procedural fever, and skin burn.

Recording of Adverse Events

At each contact with the subject, the investigator will seek information on adverse events by specific questioning and, as appropriate, by examination. Information on all adverse events will be recorded immediately in the source document, and also in the appropriate adverse event section of the case report form (CRF). All clearly related signs, symptoms, and abnormal diagnostic procedures results will also be recorded in the source document.

The clinical course of each event will be followed until resolution, stabilization, or until it has been determined that the study treatment or participation is not the cause. Serious adverse events that are still ongoing at the end of the study period will be followed up to determine the final outcome. Any serious adverse event that occurs up to 30 days after the subjects final study visit, and is considered to be related to or possibly related to the study treatment or study participation, will be recorded and reported immediately.

Reporting of Serious Adverse Events

Notification to Data Coordinating Center

A Serious Adverse Event (SAE) form must be completed by the investigator and emailed to the DCC within 24 hours. The investigator will keep a copy of this SAE form on file at the study site. Report serious adverse events by email to:

[name] – [contact]

[name] – [contact]

At the time of the initial report, the following information should be provided:

- Study identifier
- Study Center
- Subject number
- A description of the event
- Date of onset
- Current status
- Whether study treatment was discontinued
- The reason why the event is classified as serious
- Investigator assessment of the association between the event and study treatment

Within the following 48 hours, the investigator must provide further information on the serious adverse event in the form of a written narrative. This should include a copy of the completed Serious Adverse Event form, and any other diagnostic information that will assist the understanding of the event. Significant new information on ongoing serious adverse events should be provided promptly to the DCC.

DATA SAFETY MONITORING

The Data Safety Monitoring Board (DSMB) is the primary data and safety advisory group for the **Female Foundation for Health Awareness (FFHA)** trial entitled "**A Randomized Clinical Trial Comparing Vaginal Laser Therapy to Vaginal Estrogen Therapy (VeLVET) in Women with Genitourinary Syndrome of Menopause (GSM)**". The DSMB reviews study data, evaluates the treatments for excess adverse experiences according to treatment group, judges whether the overall integrity and conduct of the study remain acceptable and makes recommendations to the FFHA and the Cleveland Clinic Data Coordinating Center.

- The DSMB will consist of 3 members that are not participating in this trial. All members have experience and expertise in their field of practice and in the conduct of clinical trials. Members were selected by the Cleveland Clinic Data Coordinating Center in conjunction with [name] [name]., Principal Investigator, Co-Investigators of the study and the FFHA.
- The DSMB will meet via teleconferences after 5 subjects from each site is enrolled, or sooner if warranted.
- During the initial portion of the conference call, members of the operational team will give an overview of the status of the trial and be available to answer questions from DSMB members. The Cleveland Clinic DCC will provide a general study status update and enrollment update at the beginning of the call. On conference calls, the Cleveland Clinic DCC will describe the reports to members. The Cleveland Clinic DCC will be present for the presentation of results and entire discussion portion of all calls to answer questions. He/she will not be present for the DSMB discussion and vote. Only voting members of the DSMB and the Cleveland Clinic DCC recorder may be present during the presentation of results and actual vote.
- After each conference call, the Cleveland Clinic DCC recorder, [name], reviewed by [name], and distributed to the DSMB, will prepare minutes. The Chairperson will send a letter to the Cleveland Clinic DCC recommending changes and continuation/discontinuation of the trial. At the end of the study, a copy of the minutes will be forwarded to the Cleveland Clinic DCC for archive.

References:

1. van der Laak JA, de Bie LM, de Leeuw H, de Wilde PC, Hanselaar AG. The effect of Replens on vaginal cytology in the treatment of postmenopausal atrophy: cytomorphology versus computerised cytometry. *J Clin Pathol*. 2002;55:446-51.

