Appendix

Baseline Examination Data

Pt. ID # _____

Treatment Group

Vaginal Laser Vaginal Estrogen

Age _____ BMI _____

Race

Caucasian African-American Hispanic Asian

Other, specify _____

Marital status

Single Married Divorced Widowed

Menopausal Status

Premenopausal Perimenopausal Postmenopausal (no menses for 6 months)

Current use of oral or transdermal hormonal therapy

Yes No

History of vaginal estrogen use

Yes No

Sexually active

Yes No

Exam:

Vaginal pH _____

Vaginal caliber XS S M L XL

Maturation Index Results:

_____ Data prior to and after Vaginal Laser or Vaginal Estrogen therapy (6 wk, 3 mos, 6 mos):

Exam

Vaginal pH _____

Vaginal caliber XS S M L XL

Local anesthetic used? Yes No N/A (Estrogen arm)

Vulvovestibular laser therapy? Yes No N/A (Estrogen arm)

Adverse event laser arm:

Inability to complete the procedure due to discomfort or constricted vagina

Yes No

Other: Specify _____

PATIENT ID: _____

PATIENT GLOBAL IMPRESSION OF IMPROVEMENT

Patient Global Impression of Improvement

Circle how you feel your symptoms are after treatment:

Much Worse	Worse	Same	Better	Much Better
1	2	3	4	5

Level of satisfaction after treatment

How would you define the level of satisfaction with the treatment?

Very Dissatisfied	Dissatisfied	Same	Satisfied	Very Satisfied
1	2	3	4	5

10 cm VISUAL ANALOG SCALE (VAS)

0 indicating absent symptoms (no bother) and 10 indicating the worst the symptoms could be (bothers as much as you can imagine). Please indicate your degree of bother with an X marked on the 10 cm line below next to each symptom.

	No Bother	Mild Bother	Moderate Bother	Most Bother
Vaginal dryness	0			10
Vaginal itching	0			10
Vaginal irritation	0			10
Painful urination	0			10

Additional question regarding sexual function not included in the FSFI.
This question will be asked at baseline, 6 weeks, 3 months, and 6 months.

Over the past 4 weeks have you been sexually active? (yes/no)

The reason if your answer no

- no partner
- no interest
- due to pain
- due to other reason, please specify_____

VAGINAL HEALTH INDEX SCALE

	Overall elasticity*	Fluid secretion type & consistency	pH	Epithelial mucosa	Moisture
1	None	None	6.1	Petechiae noted before contact	None, mucosa inflamed
2	Poor	Scant, thin yellow	5.6 – 6.0	Bleeds with light contact	None, mucosa not inflamed
3	Fair	Superficial, thin white	5.1 – 5.5	Bleeds with scraping	Minimal
4	Good	Moderate, thin white	4.7 – 5.0	Not friable, thin mucosa	Moderate

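### The dilator caliber scale has no level for a woman who cannot comfortably take the smallest size, so her result at the worst end of secondary outcome 4 is undefined

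*Combined protocol and SAP*

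**What the plan says.** Study Outcomes lists as the fourth secondary outcome "The effect of treatment on vaginal wall elasticity, using standard vaginal dilators to determine vaginal caliber".

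Vaginal examinations sets the recorded value by this rule (last two words omitted): "The investigator will determine the largest dilator of the five sizes available (XS, S, M, L, XL), that the subject can comfortably have placed in". It then adds a pain rating: "The subject then assesses how much pain she is experiencing when the dilator is placed in her vagina, using a 5-point Likert scale". The Calendar of Study Procedures schedules calibration at baseline, 6 weeks, 3 months and 6 months.

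In the Appendix, the baseline sheet and the follow-up sheet each carry the field "Vaginal caliber XS S M L XL". Neither has a box for none, unable or not done.

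Data Collection & Management lists, among the events recorded during the procedure, "inability to complete the procedure due to discomfort or constricted vagina". The follow-up sheet repeats that item under the label "Adverse event laser arm".

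The Analysis Plan assigns secondary outcomes to the intent-to-treat population and ordinal data to the Wilcoxon rank sum test. It gives no rule for a caliber that cannot be obtained.

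**The concern.** The scale is closed at the bottom. The rule asks for the largest size that is comfortable, and if no size is comfortable it has no answer. That is a result, and the worst one possible, but there is nowhere to put it.

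An examiner facing a five-box field is left with two obvious entries, and each has a cost.

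- **Blank.** The woman leaves the comparison because of her result. Every value lost this way lies at the same end of the scale, and afterwards the blank cannot be told from a skipped examination.
- **XS.** This contradicts the comfort rule. A woman who goes from tolerating none to tolerating XS, or the reverse, then shows no change.

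Six sites could settle this differently, and neither entry can be reliably undone once the data are in.

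**Working it through.** **Does any other part of the plan supply the missing value?**

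| Place | What it offers | Does it fill the gap? |
|---|---|---|
| Vaginal examinations, caliber rule | Five sizes, XS to XL | No level below XS |
| Appendix, baseline and follow-up sheets | The same five boxes | No |
| Pain rating at calibration | Score given once a dilator is in place | No score if none is placed |
| Constricted-vagina item | Laser procedure not completed | Laser arm only; about the laser procedure, not the dilator |
| Eligibility criteria | No limit on caliber or on tolerance of a dilator | Such women can be enrolled |
| Analysis Plan | Intent to treat; Wilcoxon for ordinal data | No rule for an unobtainable value |

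The count is five levels and no code for none tolerated.

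**How much could it matter?** The plan states no figure to reproduce here. It gives no share of women below XS, no distribution of sizes and no expected shift, so all three are assumed.

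Method: caliber is cut from a latent normal variable, one arm is shifted by 0.5 SD, and the arms are compared by a two-sided 5% Wilcoxon test. Each simulated trial is analysed three ways: with a sixth lowest level, with those women merged into XS, and with those women left out.

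*Setting B*: 85 per arm (the evaluable number in Sample Size Rationale), 2,000 runs. A share f of the worse arm is below XS and the rest is spread equally over the five sizes. The share below XS in the other arm is Φ(z_f − 0.5).

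| f, worse arm | Women of 85 | Other arm | Sixth level | Merged with XS | Left out | Loss if left out |
|---|---|---|---|---|---|---|
| 2% | 1.7 | 0.5% | 86.4% | 86.0% | 83.8% | 2.6 |
| 5% | 4.25 | 1.6% | 86.4% | 85.4% | 79.0% | 7.4 |
| 10% | 8.5 | 3.7% | 85.3% | 85.0% | 74.1% | 11.2 |
| 20% | 17 | 9.0% | 86.8% | 85.8% | 64.4% | 22.4 |

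*Setting A*: 83 per arm (196 × 0.85 = 166.6), 3,000 runs, worse-arm shares XS 15%, S 25%, M 30%, L 20%, XL the remainder.

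- At f = 2%, 5% and 10%, power is 87%, 86% and 85% with the sixth level, against 84%, 80% and 70% with those women left out: losses of 3, 6 and 15 points.
- The mean difference in size steps is 0.58, 0.59 and 0.55 with the sixth level; 0.55, 0.50 and 0.40 left out; and 0.57, 0.55 and 0.48 merged.
- At 10% these shares leave nothing for XL (10 + 15 + 25 + 30 + 20 = 100), so the 15-point figure comes from an extreme distribution. Setting B gives 11.2 at the same f.

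*Rarer cases*, same 0.5 SD shift: at f = 0.5% power is 85.4% against 84.7% left out (loss 0.7), and at f = 1% it is 86.8% against 85.7% (loss 1.1).

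*Smaller shift*, setting B at 0.3 SD: power falls from 45.8% to 42.2% at f = 2% (loss 3.6), and from 45.1% to 32.8% at f = 10% (loss 12.3).

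The simulation error of one power figure is about 0.9 points (√(0.79 × 0.21 / 2000) = 0.009). The differences within a row are more precise, because the three analyses use the same simulated women.

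**The case against.** The best case against this point is that the gap may rarely be met and is partly covered.

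- **The evidence that such women will enrol is indirect.** The constricted-vagina item concerns a laser probe passed to the top of the canal. The documents give no dimensions for that probe or for the XS dilator, so failing one does not show failing the other. The entry requirement of dryness of at least 7 cm is a bother score and does not measure caliber. Excluding lichen sclerosis, lichen planus and pelvic radiation, and requiring willingness to use an intravaginal product, may make such women less common. This stands. It limits how often the gap matters, but none of these criteria closes it.
- **The appendix sheets may not be the whole case report form.** They have no field for the calibration pain rating, which the protocol requires. Data Collection & Management refers to a study-specific REDCap dictionary that is not included. A reader might infer that no code exists anywhere; the documents show this only for the protocol rule and the printed sheets.
- **Other measures see part of the same problem.** The Vaginal Health Index grades elasticity from none upwards at the same four visits, and the sexual activity question offers pain as a reason. A reader might infer that treatment failure would be hidden from the trial. That goes too far: it could be obscured in the caliber outcome, not in every outcome.
- **An examiner could write a comment.** True, but a comment reaches the analysis only if someone has decided how to code it.

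**Conclusion.** The point holds as a minor one. Under the rule as written, a woman who cannot comfortably take XS has no caliber value, and nothing else in the documents supplies one for both arms.

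A reader might infer that these women will in fact be dropped or merged with XS. The documents say neither. These are the two likely entries in a five-box field, not stated practice.

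A reader might also take the power figures as the trial's expected loss. They are illustrations that rest on an assumed share below XS, an assumed spread of sizes and a true 0.5 SD shift between arms. On those terms the loss from leaving the women out is about 1 point at 0.5–1% and about 3 to 15 points at 2–10%. Merging with XS costs at most about 1 point of power; its harm is an inaccurate record and a somewhat smaller difference in size steps.

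One of nine secondary outcomes is involved, and the plan states no power target for it. The primary dryness VAS, the non-inferiority margin and the sample size are untouched.

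**What to change.** 1. Add a sixth, lowest code, XS not comfortably tolerated, to the caliber rule under Vaginal examinations and to the caliber field on both appendix sheets. Add it to the database field as well if that mirrors the sheets. Use it in both arms at all four visits.
2. Add a separate entry for calibration not done, with a reason, so that a blank no longer has two meanings.
3. State that the calibration pain rating is recorded as not applicable when no dilator is placed.
4. State in the Analysis Plan that the new code ranks below XS in the Wilcoxon comparison and stays in the intent-to-treat set.

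The cost is two tick-boxes on each of two sheets, a few sentences of text and, if needed, the matching database codes. No examination is added, and the planned test takes a sixth ordered level without change. If enrolment has begun, add the codes from now on and ask sites what past blanks and XS entries meant while source notes can still answer.
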